#### 14.9.4. ACCEPTABLE/UNACCEPTABLE FOODS AND LIQUIDS

##### Acceptable soft foods for RP103 dosing:

Applesauce (not compote, not chunky), non-dairy pudding, or berry jelly.

##### Acceptable liquids for RP103 dosing:

Fruit juice, e.g., orange juice (preferred), apple juice or any acidic fruit juice, PolyCitra, PolyCitra-K, non-caffeinated soda (allow bubbles to disperse so that soda is somewhat flat), or bottled or tap water with lemon concentrate added ( $\frac{1}{4}$  teaspoon concentrate per  $\frac{1}{4}$  ounce water / 1mL lemon concentrate per 7mL water).

##### Unacceptable foods and liquids for RP103 dosing:

Milk, dairy products, alcoholic beverages, liquids or foods with a pH from neutral to basic (e.g., bottled or tap water without lemon concentrate added).

## ABBREVIATIONS

Abbreviation	Definition
AE	Adverse Event
ATC-4	Anatomical Therapeutic Chemical 4 th Level
BMI	Body Mass Index
BSA	Body Surface Area
CSR	Clinical Study Report
ECG	Electrocardiogram
eCRF	electronic Case Report Form
eGFR	estimated Glomerular Filtration Rate
ICH	International Conference on Harmonisation
MedDRA	Medical Dictionary for Regulatory Activities
NDA	New Drug Application
NDS	New Drug Submission
[REDACTED]	[REDACTED]
PK	Pharmacokinetic
PD	Pharmacodynamic
PT	Preferred Term
SAP	Statistical Analysis Plan
SD	Standard Deviation
[REDACTED]	[REDACTED]
SOC	System Organ Class
[REDACTED]	[REDACTED]
WHO	World Health Organization

## 1. INTRODUCTION AND OBJECTIVES OF ANALYSIS

### 1.1. Introduction

This is a long-term, single-arm, open-label study of the safety, tolerability and steady-state pharmacokinetics and pharmacodynamics of RP103 in pediatric and adult subjects with cystinosis. Subjects who will have completed the last visit of the previous phase III Study (RP103-03) have been offered the opportunity to enroll in this extension study. Additional subjects, who did not complete the RP103-03 study, may have been enrolled after completion of the analysis of the RP103-03 study where the non-inferior efficacious and safe dose of RP103 versus Cystagon® has been determined.

### 1.2. Objectives of Statistical Analysis

The objective of this Study is to assess the long-term safety, tolerability, pharmacokinetics and pharmacodynamics of RP103 in pediatric and adult subjects with cystinosis.

The primary objective is to assess safety and tolerability of long-term repeat dosing of RP103 in subjects with cystinosis.

Secondary objectives include assessment of steady-state pharmacokinetics (PK) and pharmacodynamic (PD) of RP103 and [REDACTED]

This statistical analysis plan (SAP) describes the efficacy and safety analyses that will be performed, based on the study protocol amendment 9 dated 18NOV2015. This amendment (Version 2.0) of the SAP adds details about the statistical analysis to be performed. Changes from Version 1.0 of the SAP including the following:

- updated Sponsor from Raptor Therapeutics to Horizon Pharma
- updated protocol version for study
- added a description of visit windowing and visit mapping methods
- added a description of variables to be summarized for subject disposition
- added variables to be summarized for demographics and baseline characteristics
- added a summary of protocol deviations
- added details for pharmacokinetic and pharmacodynamics summaries
- [REDACTED]
- [REDACTED]
- added a summary of study drug exposure
- added details for adverse event summaries
- added details for summaries of other safety parameters including labs (added shift tables), ECG, vital signs, and concomitant medications

Any changes from the SAP will be described in the clinical study report (CSR).

## 2. STUDY DESIGN

### 2.1. Synopsis of Study Design

This is a long-term, open-label study of the safety, tolerability and steady-state pharmacokinetics and pharmacodynamics of RP103 in pediatric and adult subjects with cystinosis. Initially only subjects who completed the previous phase III Study (RP103-03) will be offered the opportunity to enroll in this extension Study.

Additional subjects, who did not complete Study RP103-03 but qualify for RP103-04 based on current inclusion and exclusion criteria, may be enrolled after completion of the analysis of the RP103-03 study where the non-inferior efficacious and safe dose of RP103 versus Cystagon® has been determined.

Study visits consist of:

#### For subjects who completed Study RP103-03:

- Screening Visit: The RP103-04 Screening visit occurred simultaneously with the RP103-03 Period 2 Day 7 End of Study (EOS) visit. These subjects continued RP103 Q12H treatment at the last dose level prescribed during their participation in Study RP103-03.
- Monthly Study Visits are only for subjects who completed Study RP103-03 and began within 1 month ( $\pm$  7 days) after study entry. Each subject completes a minimum of six (6) consecutive monthly visits.
- Quarterly Study Visits commence for each subject  $\geq$  1 month and  $<$  4 months after the subject has completed at least six (6) consecutive Monthly visits. Each Quarterly visit takes place by the middle of the first month ( $\pm$  7 days) of each calendar quarter (i.e. January 15, April 15, July 15 and October 15).
- End of Study (EOS) Visit is conducted within 7 ( $\pm$  2) days from the last completed study visit or from the date of decision to terminate.

#### For subjects who did not complete Study RP103-03:

- Screening Visit which may occur up to 28 days prior to Day 1.

- Dose Confirmation Period (Days 1-5) which includes three (3) study visits over five (5) days.
  - Day 1 includes a morning study visit while the subject is fasted, with pre-dose blood samples collected for trough cysteamine and peak white blood cell (WBC) cystine determination while the subject is still taking Cystagon®. RP103 treatment regimen begins at the clinic on the morning of Day 1, administered Q12H at a starting total daily RP103 dose equal to 70% of the Screening total daily Cystagon® dose. Subjects leave the clinic for Days 2-3 and take RP103 as instructed.
  - Days 4 and 5 each include a morning study visit; RP103 Q12H treatment regimen continues.
- Quarterly Study Visits commence for each subject  $\geq$  1 month and  $<$  4 months after enrollment in the study. Each quarterly visit takes place by the middle of the first month ( $\pm$  7 days) of each calendar quarter (i.e., January 15, April 15, July 15 and October 15).
- End of Study (EOS) Visit will be conducted within 7 ( $\pm$  2 days) from the last completed study visit or from the date of decision to terminate.

## **2.2. Randomization Methodology**

This is a single-arm study. Subjects are not randomized.

## **2.3. Stopping Rules and Unblinding**

This is an open-label, long-term safety study with no stopping rules.

## **2.4. Study Procedures**

The schedule of assessments, as outlined in the study protocol, is provided in Table 1.1 and Table 1.2.

**Table 1.1 Schedule of Events (All Subjects)**

Procedure	Screening a	Dose Confirmation Period		Visit Frequency		End of Study f
Study Visit	Day -28 to -1	Day 1 b	Day 4 and Day 5	Monthly d (± 7 days)	Quarterly e (± 7 days)	7 (± 2) days after last visit, or decision to terminate
Number of Study Visits	1	1	2	6 to 9	5 to 6	1
Informed Consent	X					
Inclusion/Exclusion	X	X c				
Demographics	X g					
Medical History	X g	X c				
Medication History	X g	X c				
Menstrual Cycle History (females of child-bearing potential only)	X g	X c				
Serum Pregnancy Test (females with childbearing potential only)	X	X c		X	X	
Body height	X	X c		X	X	X
Body weight	X	X c		X	X	X
BMI calculations	X	X c		X	X	X
BSA calculations	X	X c		X	X	X
Physical Examination i	X h	X c		X	X	X
Clinical Laboratory Test: Hematology, Chemistry, Urinalysis j	X h	X c		X	X	X
ECG k	X h	X c		X	X	X
Vital signs l	X h	X	X	X	X	X
	X	X c		X	X	X
	X	X c		X	X	X
Daily diary: training	X					
Daily Diary: medications	X	X		X	X	

Daily Diary: collection		X		X	X	X
Food/liquid intake control s		X c	X	X	X	X
Q12H RP103 administration o	X h	X	X	X	X	
WBC Cystine (PD) sample collection p collection	X	X c	X (post-dose)	X	X	X
Cysteamine (PK) sample collection q	X	X	X (post-dose)	X	X	X
Investigator Review of Safety and PK/PD data r			X	X	X	
Concomitant medications	X	X	X	X	X	X
Adverse event monitoring	X	X	X	X	X	X

- a. For subjects completing Study RP103-03, Screening can be performed concurrent with the RP103-03 End of Study Visit and will be considered Day -1 for this Study. For subjects that did not participate in the RP103-03 study, Screening can take place up to 28 days prior to the first Study visit (Day 1).
- b. Day 1 Visit is only to be performed for subjects that did not complete Study RP103-03.
- c. These procedures were should have been performed at Screening and are to be repeated only if the Day 1 visit occurs more than 7 days after the Screening visit.
- d. A minimum of 6 consecutive Monthly ( $\pm$  1 week) Visits will be conducted for all subjects who completed Study RP103-03 prior to enrolling in study RP103-04. Subjects who did not complete Study RP103-03 will not attend Monthly visits.
- e. Quarterly visits will take place by the middle of the first month ( $\pm$  7 days) of each calendar quarter (i.e., January 15, April 15, July 15 and October 15) so that samples can be analyzed on the bioanalytical lab's quarterly analysis schedule.
- f. The End of Study visit will be conducted within 7 ( $\pm$  2 days) from the last completed study visit or from the date of decision to terminate.
- g. For subjects that completed the RP103-03 Study, data can be obtained from the RP103-03 Screening visit.
- h. For subjects that completed the RP103-03 Study, data can be obtained from the RP103-03 End of Study Visit.
- i. Physical examinations are to include standard physical assessments together with a neurological and skin examination.
- j. Clinical laboratory (chemistry and hematology) and urinalysis samples will be collected at Screening (if required) and at Monthly and Quarterly visits, thereafter and at the End of Study (EOS) visit.
- k. 12-lead ECG will be collected within 30 minutes prior to Study drug administration at Screening (if required) and at Monthly and Quarterly visits, thereafter and at the End of Study (EOS) visit. For subjects that did not complete Study RP103-03, the 12-lead ECG will also be conducted at approximately 3 hours ( $\pm$  15 minutes) post RP103 dose on Day 1.
- l. Vital signs will be measured within 30 minutes prior to Study drug administration at Screening (if required) and at Monthly and Quarterly visits, thereafter and at the End of Study (EOS) visit. For subjects that did not complete Study RP103-03, vital signs will also be repeated 30 minutes prior to Study drug administration on Day 1.

- o. RP103 will be administered Q12H daily. Subjects that completed Study RP103-03 will continue to receive their Q12H RP103 dose determined during that Study. For subjects that did not complete Study RP103-03, the first dose of RP103 will be given on Day 1, with a starting Q12H RP103 dose at a total daily dose which is 70% of their total daily dose Cystagon® dose.
- p. A PD (WBC cystine) sample will be collected at: Screening, (if subject did not complete Study RP103-03) at 5-6 hours after the last Cystagon® dose, on Day 1 (if subject did not complete Study RP103-03) immediately prior ( $\leq$  15 minutes) to morning dose administration of RP103, and for all subjects at 0.5 hour (30 minutes) post RP103

---

dose on Monthly and Quarterly Visits, thereafter and at the End of Study (EOS) visit. For subjects who have transitioned back to Cystagon®, the EOS visit PD blood sample will be collected immediately prior to their next Cystagon® dose.

- q. A PK (plasma cysteamine) sample will be collected at: Screening (if subject did not complete Study RP103-03) at 5-6 hours after the last Cystagon® dose, on Day 1 (if subject did not complete Study RP103-03) immediately prior ( $\leq$  15 minutes) to morning dose administration of RP103, and for all subjects at 0.5 hour (30 minutes) post RP103 dose on Monthly and Quarterly Visits, thereafter and at the End of Study (EOS) visit. For subjects who have transitioned back to Cystagon® PK blood sample at the EOS visit will be collected immediately prior to their next Cystagon® dose.
- r. Investigator will perform a review of available safety, PK and PD data prior to or at study visits (i.e., Monthly/Quarterly). A dose adjustment may be indicated, as described in Section 8.5 of the protocol. For subjects who did not complete Study RP103-03, the first potential dose adjustment should be as soon as the Investigator receives WBC cystine results for the Dose Confirmation Period, so that any RP103 dose adjustment may be implemented before the subject returns for their next study visit (Quarterly Visit 1).
- s. Food should try to avoid eating food for at least 2 hours before and 30 minutes after RP103 administration. In case subjects cannot comply with this recommendation, they should ingest at least a small amount of food around the time of RP103 dosing (from 1 hour before to 1 hour afterwards).

## 2.5. Study Endpoints

### 2.5.1. Safety Endpoints

The safety profile of RP103 is investigated by safety reviews conducted by the Investigator at or prior to each monthly or quarterly visit and through adverse event report monitoring (including attribution of treatment-emergent adverse events and serious adverse events [SAEs]), physical examination (including basic neurological and skin assessment findings), vital signs, 12-lead electrocardiogram (ECG) and clinical laboratory testing as outlined in the Schedule of Events.

### 2.5.2. Pharmacokinetic Endpoints

The trough plasma cysteamine concentration is measured from samples collected 0.5 hour post dose at each study visit.

### 2.5.3. Pharmacodynamic Endpoints

The WBC cystine content is measured from samples collected 0.5 hour post dose at each study visit.

### **3. SUBJECT POPULATIONS**

#### **3.1. Population Definitions**

Two populations for this study are planned for analysis as described below.

**Safety Population:** The Safety Population consists of all subjects who received at least one dose of study drug (RP103).

**PK/PD Population:** All subjects who have at least one PK/PD measurement are included in the PK/PD population.

Each one of these 2 populations is then partitioned in 3 subpopulations:

A: Subjects who completed Study RP103-03

B: Subjects  $\leq$  6 years old

C: Renal Transplant subjects

#### **3.2. Protocol Violations/Deviations**

Failure to meet any inclusion or exclusion criteria (see Sections 7.1 and 7.2 of the protocol) during participation in the study constitutes a protocol violation. Other unforeseen situations may result in a protocol violation and is reported accordingly. No protocol violations are used to exclude subjects from the safety analysis.

### **4. STATISTICAL METHODS**

#### **4.1. Sample Size Justification**

The sample size for this study is determined by the number of subjects who participated in the previous phase III Study (RP103-03) and any additional subjects, who did not complete the RP103-03 study, who enroll after all subjects that participated in RP103-03 completed and data have been analyzed.

#### **4.2. General Statistical Methods and Data Handling**

##### **4.2.1. General Methods**

All data displays and analyses will adhere to the International Conference on Harmonisation (ICH) recommendations, and will be formatted to the appropriate page size(s).

Tabulations will be produced for appropriate demographic, baseline, efficacy, and safety parameters. For categorical variables, summary tabulations of the number and percentage within each category (with a category for missing data) of the parameter will be presented. For continuous variables, N, the mean, median, standard deviation, minimum and maximum values

---

will be presented.

Relative days will be calculated relative to the first dose of study drug. Day 1 will be the first day of study drug administration in the study, and the day prior to the first dose of study drug administration will be Day -1. There will be no Day 0.

Any statistical testing will be considered exploratory; two-sided p-values will use alpha = 0.050.

Baseline is defined, unless otherwise specified, as the last non-missing measurement before the first dose of study drug, unless otherwise specified. For subjects who completed Study RP103-03, baseline results could come from the Screening Visit (which is the RP103-03 Period 2 Day 7 End of Study (EOS) visit).

#### 4.2.2. Computing Environment

All descriptive statistical analyses will be performed using SAS statistical software (Version 9.2 or later), unless otherwise noted. Medical history and adverse events will be coded using Medical Dictionary for Regulatory Activities (MedDRA), Version 13.0. Concomitant medications will be coded using the World Health Organization (WHO) Drug Dictionary (June 2010).

#### 4.2.3. Methods of Pooling Data

Not applicable to the present study.

#### 4.2.4. Adjustments for Covariates

There are no planned adjustments for covariates in this study.

#### 4.2.5. Multiple Comparisons/Multiplicity

No formal statistical adjustments are planned for multiplicity.

#### 4.2.6. Subpopulations

Data will be summarized by the subpopulations described in Section 3.1:

- A: Subjects who completed Study RP103-03
- B: Subjects  $\leq$  6 years old
- C: Renal Transplant subjects

---

#### 4.2.7. Withdrawals, Dropouts, Loss to Follow-up

---

There are no planned exclusions due to withdrawals, dropouts, or loss to follow-up.

#### 4.2.8. Missing, Unused and Spurious Data

Imputation of missing data is not planned.

#### 4.2.9. Visit Windows

The visit schedule in Study RP103-04 differed according to whether a subject entered the study after completing Study RP103-03 or entered the study without having previously participated in Study RP103-03 (i.e., Subjects  $\leq$  6years of age and kidney transplant recipients). This difference in visit schedule resulted in each Quarterly visit for subjects from Study RP103-03 occurring, on average, approximately 6 months later in the study than the corresponding Quarterly visit for subjects who did not previously participate in Study RP103-03. For example, the Quarterly 1 visit of a subject from Study RP103-03 generally occurred at approximately 0.75 years in the study, while the Quarterly 1 visit for a subject not previously participating in Study RP103-03 generally occurred at approximately 0.25 years in the study. Two approaches were taken in the analysis to aligning visits for summarization over time:

1. **Collected Visits:** Scheduled Visits (i.e., the visit as recorded on the case report form) were assigned to what is referred to as “Collected Visits” (see
2. Table 2). Summarization using Collected Visits will help to address the approximate 6-month difference between the Quarterly visits for subjects from Study RP103-03 compared to subjects who had not participated in Study RP103-03.

**Table 2: Definition of “Collected Visits” for Subjects Not Previously Participating in Study RP103-03 (Subjects  $\leq$  6 Years of Age and Kidney Transplant Recipients)**

Scheduled Visit		Assigned “Collected Visit” (Label)
Scheduled Visit Number	Scheduled Visit Name	
14	Quarterly 1	Monthly 3
15	Quarterly 2	Monthly 6
16	Quarterly 3	Quarterly 1
17	Quarterly 4	Quarterly 2
18	Quarterly 5	Quarterly 3
19	Quarterly 6	Quarterly 4
20	Quarterly 7	Quarterly 5
21	Quarterly 8	Quarterly 6
22	Quarterly 9	Quarterly 7
23	Quarterly 10	Quarterly 8
24	Quarterly 11	Quarterly 9

Scheduled Visit		Assigned “Collected Visit” (Label)
Scheduled Visit Number	Scheduled Visit Name	
25	Quarterly 12	Quarterly 10
26	Quarterly 13	Quarterly 11
27	Quarterly 14	Quarterly 12
Continues in this pattern for however many Quarterly visits occur		

The table only displays Collected Visits for which the name/label differs from that of the Scheduled Visit.

3. **Analysis Visits:** Based on the assessment date, the Study Day of each visit of a given subject (where Study Day 1 is the first day of dosing with RP103 in Study RP103-04) will be assigned to the Study Month in which it occurred, based on a window around a scheduled timepoint. This approach of summarizing by month is referred to as summary based on “Analysis Visits.” Because visits were generally scheduled quarterly rather than monthly, there may be more fluctuation in sample sizes over time for Analysis Visits than for Scheduled or Collected Visits. Details of the windowing are below.

The following time windows will be used to assign an assessment, including unscheduled assessments, to a month.

Visit	Scheduled Study Day	Time Window
Month 1	30	> 1 - ≤ 45
Month 2	60	> 45 - ≤ 75
Month 3	90	> 75 - ≤ 105
Month 4	120	> 105 - ≤ 135
Month 5	150	> 135 - ≤ 165
Month 6	180	> 165 - ≤ 195
Month 7	210	> 195 - ≤ 225
Etc.		

If more than one assessment is included in a time window, then the assessment performed closest to the Scheduled Study Day will be used in analyses. When more than one day is of equal proximity to the Scheduled Study Day, then the data collected after the Scheduled Study Day will be used in analyses.

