## 8. PHARMACOKINETIC, PHARMACODYNAMIC AND

### 8.1. Pharmacodynamics

WBC cystine concentration levels (nmol  $\frac{1}{2}$  cystine/mg) will be summarized over time using descriptive statistics (number of subjects, mean, geometric mean, median, standard deviation, coefficient of variation, minimum, and maximum) for the PK/PD Population for each subpopulation and overall. Summaries will be provided for both analysis visits and collected visits. WBC cystine concentration levels will also be summarized over time by baseline WBC cystine levels ( $\leq 1$ ,  $> 1$  to  $\leq 2$ ,  $> 2$  nmol  $\frac{1}{2}$  cystine/mg) for both analysis visits and collected visits.

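### The SAP month windows place PK/PD samples by date alone, so an End of Study sample taken on Cystagon can be summarised as an RP103 value

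*SAP*

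**What the plan says.** **Endpoints.** SAP 2.5.3 states: "The WBC cystine content is measured from samples collected 0.5 hour post dose at each study visit". SAP 2.5.2 sets the same time for plasma cysteamine. Neither names the product.

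**EOS samples.** Protocol 9.1.6 gives two PK/PD instructions. Patients still on RP103 are sampled half an hour after an RP103 dose. Patients who have moved to Cystagon are sampled just before their next Cystagon dose. The Cystagon instruction also appears in the protocol synopsis, in 6.1.2, and in footnotes p and q of both the protocol and SAP schedules. EOS falls 7 ± 2 days after the last completed visit or after the decision to terminate.

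**Assignment to months.** The Analysis Visit rule in SAP 4.2.9 starts "Based on the assessment date, the Study Day of each visit of a given subject" and places that day in a Study Month. It adds: "The following time windows will be used to assign an assessment, including unscheduled assessments, to a month". If a window holds more than one assessment, "then the assessment performed closest to the Scheduled Study Day will be used in analyses". A tie goes to the one after the scheduled day.

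**Population and summaries.** SAP 3.1: "All subjects who have at least one PK/PD measurement are included in the PK/PD population". SAP 4.2.7: "There are no planned exclusions due to withdrawals, dropouts, or loss to follow-up". SAP 8.1, and 8.2 in the same words: "Summaries will be provided for both analysis visits and collected visits". The readable text of these two sections states no treatment condition. SAP 9.1, by contrast, subtracts days on Cystagon from RP103 exposure.

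**The concern.** PK and PD of RP103 are a stated secondary objective, and the month tables are where a reader would look for long-term WBC cystine on RP103. Under the rule as written, one row can combine samples taken half an hour after RP103 with a sample taken at the end of a Cystagon dosing interval. Nothing in the readable text says such a value would be flagged. Where the Cystagon sample lies nearer the scheduled day, it also removes an on-RP103 value from a patient who stopped RP103.

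The exposure calculation shows that time on Cystagon within the study was foreseen and handled in one place. There is no matching rule for PK/PD. The weight of a single value is largest in sparsely filled months, and SAP 4.2.9 itself warns that sample sizes may fluctuate more across Analysis Visits.

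**Working it through.** The plan gives no figure to reproduce here. The check asks how often the date rule selects an EOS sample, and how far one such value can move a mean.

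**1. Windows (SAP 4.2.9).** From Month 2 on, Month k runs from day 30k - 14 to day 30k + 15 with scheduled day 30k. This matches the SAP table: Month 2 is days 46 to 75 and Month 7 is days 196 to 225.

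**2. EOS timed from the last visit.** Let d be the last visit's offset from the scheduled day (-14 to +15, 30 positions) and L the lag to EOS.
- EOS stands alone in the next window if d + L > 15.
- EOS replaces the last visit if d + L ≤ 15 and |d + L| ≤ |d|. Equality goes to EOS because it then falls after the scheduled day.
- Otherwise EOS is not used.

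Assumption: d is equally likely to take any of the 30 values.

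| L (days) | EOS replaces | EOS alone | EOS not used | EOS used |
|---|---|---|---|---|
| 5 | 12 | 5 | 13 | 17/30 = 57% |
| 7 | 11 | 7 | 12 | 18/30 = 60% |
| 9 | 10 | 9 | 11 | 19/30 = 63% |

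So 37% to 43% of EOS samples at these lags are not selected. Three examples at L = 7:
- Visit on day 290, EOS on day 297: Month 10 takes EOS (3 days from day 300 against 10), and the day 290 value is lost.
- Visit on day 310, EOS on day 317: EOS alone fills Month 11.
- Visit on day 300, EOS on day 307: EOS is not used.

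**3. EOS timed from a decision to terminate.** This fits patients who stop between quarterly visits better. Assumption: the decision falls evenly on days 0 to 90 after a quarterly visit, with EOS g days later, so L runs from g to 90 + g. That gives 91 × 30 = 2,730 combinations. For L ≥ 30, EOS always stands alone.

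| g (days) | EOS alone | EOS replaces | EOS used |
|---|---|---|---|
| 5 | 2,405 (88.1%) | 156 (5.7%) | 93.8% |
| 7 | 2,454 (89.9%) | 132 (4.8%) | 94.7% |
| 9 | 2,499 (91.5%) | 110 (4.0%) | 95.6% |

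Here selection is near certain, but displacement of an on-RP103 value is rare.

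**4. Shift in a WBC cystine mean.** If one of n values is x where an on-RP103 value would average b, the mean moves by (x - b)/n. Inputs for Cystagon are the Study RP103-03 means in protocol 4.2.2.
- Per protocol, Cystagon 0.54 and RP103 0.62: (0.54 - 0.62)/n = -0.08/n.
- Intent to treat, Cystagon 0.97 and RP103 0.70: (0.97 - 0.70)/n = +0.27/n.
- Off drug, illustration only: the documents give no level some days after stopping. I take x from 1.0 up to 2.015, the fitted starting level in protocol Table 1 (SE 0.303, from the nine-patient pilot), with b = 0.62. This gives +0.38/n to +1.395/n.

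| n | Cystagon, per protocol | Cystagon, intent to treat | Off drug, if sampled |
|---|---|---|---|
| 10 | -0.008 | +0.027 | +0.038 to +0.140 |
| 20 | -0.004 | +0.014 | +0.019 to +0.070 |
| 60 | -0.001 | +0.005 | +0.006 to +0.023 |

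The largest n, 60, is the planned maximum enrolment. No shift is computed for plasma cysteamine, because the documents tabulate neither a pre-dose Cystagon level at 6 hours nor an RP103 level at half an hour.

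**The case against.** **The endpoint definition already excludes these samples.** A pre-dose Cystagon sample is not a half-hour post-dose sample, and the objective concerns RP103. This is the nearest thing to a condition, and it shows that pooling the products is not intended. But it is a definition, it does not name the product, and 8.1 and 8.2 do not apply it as a filter. Nor is it applied to all WBC cystine data: for patients entering on Cystagon, baseline is the last value before RP103, which is a pre-dose Cystagon sample.

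**The effect is negligible.** For Cystagon samples this largely stands. The shifts are small against the 1 nmol target in protocol 8.5 and the 0.3 margin of Study RP103-03. The intent-to-treat contrast comes from adding three poorly controlled patients, and its interval for RP103 minus Cystagon reaches +0.09, so even the sign is unsettled.

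**The 57% to 63% figures describe the wrong patients.** Partly right. Leaving 5 to 9 days after a regular visit mainly describes patients still on RP103, whose samples are valid. Step 3 fits stoppers better.

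**The rule may be in redacted text.** Text after 8.2, a bullet in SAP 10 and most of SAP 12 are blacked out, so the point covers readable text only. Section 4.2.9 and the opening statements of 8.1 and 8.2 are readable.

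**Stronger readings that a reader might infer:**
- That patients on neither product supply samples to these tables. Protocol 7.3 asks for termination assessments in general after early discontinuation, but 9.1.6 and footnotes p and q give no PK/PD instruction for such patients. An off-drug sample would enter the same way only if one were taken.
- That the Collected Visit tables and Figure 1 are mixed throughout. SAP Table 2 relabels only Quarterly visits, and its note says "The table only displays Collected Visits for which the name/label differs from that of the Scheduled Visit". EOS therefore probably keeps its own row, and any mixing stays there.
- That the protocol orders an RP103 dose at EOS for stopped patients. The synopsis and 6.1.2 are loosely worded, but 9.1.6 limits that dose to patients still on RP103, and 10.1.1 stops dosing in the cases it lists.
- That SAP 3.1 dropped a safeguard in protocol 11.2. That definition selects subjects, not samples, and protocol 11.1 lets the SAP modify the plan.

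**Conclusion.** The point holds as a gap in the readable SAP. A planned EOS sample taken on Cystagon is eligible for an RP103 month, is chosen or dropped by date alone, and can displace the patient's last on-RP103 value. It does not always enter: selection runs from 57% to 63% when EOS follows a visit by 5 to 9 days, and from 94% to 96% when it follows a decision made between quarterly visits. Both ranges rest on the even-timing assumptions stated in the check.

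The effect of a Cystagon value on a WBC cystine mean is small, at most about 0.03 nmol ½ cystine/mg protein at n = 10. The off-drug range is larger but rests on an assumed level and on samples the protocol does not specify. The number of patients returning to Cystagon is not in the documents. The tables are descriptive and serve a secondary objective, so this is a minor correction. Its value is that the tables would describe RP103 only.

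**What to change.** In SAP 8.1 and 8.2, add one sentence to each: post-baseline RP103 summaries include only samples taken after an RP103 dose in patients on continuing RP103 at that visit, and this is applied before the closest-day selection in 4.2.9. Both parts are needed, because a patient given RP103 only at the EOS visit would satisfy the first part alone. Apply the rule to every post-baseline sample in the Analysis Visit tables and to the EOS row of the Collected Visit tables. Leave baseline alone, since it is a Cystagon value by design for patients entering on Cystagon. List Cystagon samples, and any off-drug samples, separately with the product and sampling time shown.

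Take treatment status from the recorded dosing data, including the Cystagon days already needed for SAP 9.1. Use the diary as support only, because protocol 8.4 foresees diary non-compliance.

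The cost is a few non-comparable samples leaving the summaries and slightly smaller counts in some months. Where an EOS value would have displaced an on-RP103 value, the latter returns. No new data and no protocol amendment are needed.
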